## SOCIAL BEHAVIORAL INSTRUCTIONS AND TEMPLATE

NUMBER	DATE	PAGE
HRP-503a	12/21/2017	5 of 6

### 11 Privacy and Confidentiality

Describe the steps that will be taken to protect subjects' privacy interests. "Privacy interest" refers to a person's desire to place limits on with whom they interact or to whom they provide personal information. Click here for additional guidance on [ASU Data Storage Guidelines](#).

Describe the following measures to ensure the confidentiality of data:

- Who will have access to the data?
- Where and how data will be stored (e.g. ASU secure server, ASU cloud storage, filing cabinets, etc.)?
- How long the data will be stored?
- Describe the steps that will be taken to secure the data during storage, use, and transmission. (e.g., training, authorization of access, password protection, encryption, physical controls, certificates of confidentiality, and separation of identifiers and data, etc.).
- If applicable, how will audio or video recordings will be managed and secured. Add the duration of time these recordings will be kept.
- If applicable, how will the consent, assent, and/or parental permission forms be secured. These forms should separate from the rest of the study data. Add the duration of time these forms will be kept.
- If applicable, describe how data will be linked or tracked (e.g. masterlist, contact list, reproducible participant ID, randomized ID, etc.).

If your study has previously collected data sets, describe who will be responsible for data security and monitoring.

All staff will have taken the required online human subjects course on this topic. In addition, this topic will be regularly addressed during weekly staff meetings where staff will be encouraged to ask questions pertaining to this issue. All participants will receive a randomly assigned research ID number. A "key" will be maintained which links the participants to the previous identification. The key will be maintained electronically (with regularly scheduled data backups), using data encryption procedures and stored on University maintained servers with electronic firewall protection. "Strong" computer passwords will be required to gain access to the key; passwords will be changed routinely. The PI and other senior level staff will have access to the key (maintained electronically). These data will be password protected.

The local smartphone data will be stored in an SQLite database, which is an industry-standard data management strategy that encrypts data and is not accessible to others.

The master list will be destroyed immediately after data are linked. The data will be de-identified. Data will be retained up to a five years after the final publication from this work and any paper files will be shredded prior to disposal. Electronic files will be deleted from all storage sites including back-up drives.

### 12 Consent Process

Describe the process and procedures process you will use to obtain consent. Include a description of:

- Who will be responsible for consenting participants?
- Where will the consent process take place?
- How will consent be obtained?
- If participants who do not speak English will be enrolled, describe the process to ensure that the oral and/or written information provided to those participants will be in that language. Indicate the language that will be used by those obtaining consent. Translated consent forms should be submitted after the English is approved.

**SOCIAL BEHAVIORAL INSTRUCTIONS AND TEMPLATE**

NUMBER	DATE	PAGE
HRP-503a	12/21/2017	6 of 6

A short consent will be obtained before the individual completes the initial screening form online (see attachment) to determine eligibility for the study. Any identifying information obtained during this time will be retained only if the participant is eligible. If participant is eligible and interested, consent for further study participation will be obtained virtually through the use of Qualtrics.

During this consent process, individuals will specifically be asked to consent to allow the research team to gather location data as it is a particularly personal type of data being collected. Participants will also be asked if they have jailbroken their phone and to acknowledge, in writing that their phone is not jailbroken. If it is, participants will be informed of the added data security risks and asked to initial their consent to participate, knowing this added data security risk. Rooting or Jailbreaking involves allowing the user of the smartphone added privileges to the phone, similar to running programs as administrators in Windows. With a rooted (or jailbroken) phone you can run apps that require access to certain system settings. Note, rooting/jailbreaking a phone is a fairly lengthy process and thus, if the participant purchased the phone from a normal channel, such as from a cell phone company, and did not actively root/jailbreak their phone, then it is highly unlikely that the phone is rooted/jailbroken. Participants will also be told that they have the right to revoke access to these data any time during the research process.

**13 Training**

Provide the date(s) the members of the research team have completed the CITI training for human participants. This training must be taken within the last 4 years. Additional information can be found at: [Training](#).

## **Statistical analyses**

### *PART A*

All statistical analyses will be completed using SAS Version 7.1 (SAS Institute, Inc., Cary, North Carolina). Mixed model analyses will be conducted using PROC MIXED to examine the bi-directional associations of sitting, standing, and moving behaviors and affective states. All models will be adjusted for age, gender, race and job type.

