**2 Background and Objectives**

Provide the scientific or scholarly background for, rationale for, and significance of the research based on the existing literature and how will it add to existing knowledge.

- Describe the purpose of the study.
- Describe any relevant preliminary data or case studies.
- Describe any past studies that are in conjunction to this study.

The unique attributes of sedentary behavior (SB) (e.g., ubiquitous, habitual, socially-reinforced) and its link to cardiometabolic health risk have led to several studies aimed at understanding the correlates of SB. However, these studies have primarily focused on "static" correlates (e.g., built environment, income status, educational attainment, etc.) and have largely ignored the complex situational, contextual, and dynamic "in the moment" factors that can influence SB.

The development of smart phone apps and wearable devices (e.g. Fitbit, apple watch, jawbone, etc.) within the technology industry has resulted in an increase in personal notifications to stand or move more during the workday. These prompts may vary in medium (phone, email, watch), delivery (textual, visual, sound, vibration) and content (personalized, generic, short, long, motivational, educational, feedback). However, the extent to which these prompts actually reduce SB is not fully understood.

The overall objective of this set of exploratory studies is to understand the personal, behavioral, environmental, and contextual factors that underpin SB and to systematically test a series of contextual prompt characteristics that may lead to subsequent change in SB.

The primary aims are:

**Aim 1.** Using Ecological Momentary Assessment (EMA), we will determine which personal (e.g. fatigue, mood, and stress level), behavioral (e.g. watching TV, working at desk, and eating meals), environmental (e.g. being at home or work, time of the day, and weather) and contextual factors are associated with SB. We will identify the combination of factors most likely to precede and proceed short (<30 min) and long (≥30 min) bouts of SB.

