**SOCIAL BEHAVIORAL INSTRUCTIONS AND TEMPLATE**

NUMBER	DATE	PAGE
HRP-503a	12/21/2017	3 of 6

This 10-week study has 2 main parts: (A) an EMA study and (B) a Screening experiment. Twenty participants will be recruited for the study.

Prior to the start of the study, participants will first have to complete an initial online screening survey to determine eligibility. All eligible participants will be requested to complete an online consent and depending on their smartphone operating system, will be sent instructions (see appendix D, E, F, and G) on how to download the smartphone apps that will be used in the study:

Smartphone App	OS	Description
PACO	Android or iOS	An open-source app designed that will be used to deliver EMA questions randomly throughout a participant's workday.
Daynamica	Android	An app designed to collect user activity and travel data using raw smartphone accelerometer and GOS data.
Prox	iOS	An iOS app designed to capture real-time indoor (office) location through proximity sensors deployed around the workplace.

Eligible and consented participants will be invited to a one-hour orientation session where they will be given detailed information about the study, along with answering any questions or concerns they may have. During this visit, proximity sensors will also be deployed to various key areas in the workplace (i.e., participant's desk, lobby, kitchen, and conference rooms).

Timeline:

	Week									
	Part A				Part B					
Measures	1	2	3	4	5	6	7	8	9	10
Main Survey	X						X			X
Daily logs	X	X	X	X			X	X	X	X
EMA	X	X	X	X						
Prompts							X	X	X	X
ActivPAL	X	X	X	X			X	X	X	X

Throughout Parts A and B (weeks 1-10):

All participants in both part A and B will be asked to complete daily logs that will ask them of the time they went to work and got off of work the previous day, sleep time of the previous night and the time they woke up, and any work-related meetings that they had the previous day. In addition, they will be asked to complete a battery of assessment (see appendix A for list of questionnaires) at three time points in the study: at week 1, 7, and 10. Participants will also be asked to wear the activPAL device on their thigh as an objective measure of sedentary and physical activities. They will be asked to wear the device continuously throughout the study except for the interview weeks (week 5 and 6). The activPAL will be dropped off every Monday morning and picked up every Friday of the same week.

Part A (Weeks 1-4):

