**SOCIAL BEHAVIORAL INSTRUCTIONS AND TEMPLATE**

NUMBER	DATE	PAGE
HRP-503a	12/21/2017	4 of 6

Participants will receive 3 random EMAs (Appendix B) per day throughout the 4-week study. EMAs will only be sent during work hours (9AM-5PM). A total of 1200 EMA observations (3x/day x 20 work days x 20 participants) will be collected.

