### *PART B*

For instances where prompts were sent and a response occurred, the response time will be recorded (seconds) and the average response time calculated. The number of responses occurring each hour will be calculated to identify the frequency of responses by hour. Generalized estimating equations (GEEs) will be ran using GENMOD (with a repeated statement) to examine the main effect of prompt delivery (sent or not sent) by modeling the mean likelihood of a response as an odds ratio, over the next 5-minute and 30-minute periods. An autoregressive model will be used to account for time dependency and the correlation between observations. Mixed model analyses will be conducted using PROC MIXED to examine the association between prompt type and total sedentary time over the next 5-minute and 30-minute period. All models will be adjusted for age, race, gender, day of intervention and minutes of sitting 30 minutes prior to a prompt. Decision points where the participant was standing or moving at the time of prompt delivery (sent) or scheduled (not sent) time will be excluded from analyses.

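### Part A's models of behavior and affect adjust only for traits fixed within a person, so they cannot support a directional reading of the two-way association.

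*SAP*

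**What the plan says.** The SAP (Statistical analyses, PART A) plans PROC MIXED models of "bi-directional associations of sitting, standing, and moving behaviors and affective states". The adjustment is stated once: "All models will be adjusted for age, gender, race and job type". It does not say which variable is the outcome in each direction, or over which minutes before or after an EMA behavior is measured. It also does not say whether the association sought is marginal or net of earlier behavior.

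Protocol section 2 sets the purpose: "The overall objective of this set of exploratory studies is to understand" the factors behind sedentary behavior. Aim 1 asks which personal, behavioral and environmental factors, including "time of the day, and weather) and contextual factors are associated with SB". It also asks for "the combination of factors most likely to precede and proceed short" and long bouts.

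Protocol section 7 schedules three random EMAs per working day for four weeks: "EMAs will only be sent during work hours (9AM-5PM"). Behavior is recorded by activPAL in the same weeks.

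The SAP's PART B treats the matter differently. It states 5- and 30-minute windows, an autoregressive structure, and adjustment for "day of intervention and minutes of sitting 30 minutes prior to a prompt".

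**The concern.** Both variables are measured repeatedly within a person through the working day, but every listed covariate describes the person and not the moment. Three sources of association are left in.

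- **Shared clock time.** If sitting and affect both change over the day, they correlate even when neither influences the other.
- **Earlier sitting.** If sitting influences affect and sitting persists, affect will appear to predict later sitting.
- **Earlier affect.** If affect influences sitting and affect persists, sitting will appear to predict later affect.

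Any of these could be written up as a two-way relation, and a reader could not tell them apart from the models as described. Aim 1 itself names time of day and asks about what comes before and after bouts. No Part B comparison depends on these models, and neither does the stated primary outcome.

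**Working it through.** **The plan's own figure.** 3 EMAs × 20 work days × 20 participants = 1,200, as protocol section 7 states. That is 60 per person.

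**Part A beside Part B.** Part B's covariates cannot be read back into Part A. They stand under the PART B heading, refer to a prompt, and omit job type. Part A's own list is complete as written and contains nothing that varies between EMAs.

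**If behavior and affect come from the same window.** With person-demeaned data, regressing behavior on affect and affect on behavior gives one and the same t. At a within-person correlation of 0.10 with 960 records, t = 0.10 × √939 / √(1 − 0.01) = 3.08 in both directions (939 = 960 − 20 person means − 1 slope). In an uncentred random-intercept model the two are nearly but not exactly equal: simulated mean differences in |t| were 0.05 to 0.14, with a maximum of 0.7.

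**If later behavior is regressed on affect.** This reading is inferred from the SAP's term for two-way association and from Aim 1; it is not stated.

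Assumed inputs, none from the documents except where noted:
- 960 records = 20 people × 48 EMAs, where 48 is 80% of 60 (the payment threshold in protocol section 8).
- r = within-person correlation of prior sitting with affect.
- phi = correlation of prior with later sitting.
- R = correlation of time of day with each variable.
- Affect has no influence of its own.
- A 5% two-sided test. Part A states no alpha, so this is a benchmark.

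The induced correlation is d = r × phi through earlier sitting, or d = R² through time of day. The expected statistic is z = d√939 / √(1 − d²), and the rejection probability is P(Z > 1.96 − z) + P(Z < −1.96 − z).

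| Path | d | z | Rejects, formula | Rejects, person-demeaned simulation |
|---|---|---|---|---|
| r = 0.10, phi = 0.3 | 0.03 | 0.92 | 15% | 15% |
| r = 0.15, phi = 0.4 | 0.06 | 1.84 | 45% | 44–48% |
| r = 0.20, phi = 0.5 | 0.10 | 3.08 | 87% | 87% |
| R = 0.2 | 0.04 | 1.23 | 23% | 24% |
| R = 0.3 | 0.09 | 2.77 | 79% | 78% |

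Adding prior sitting in the first three rows, or time of day in the last two, brings the simulated rate back to 4–6%. Rejection passes 10% at d of about 0.021 and 50% at about 0.064. Below that the effect is minor: r = 0.05 with phi = 0.2 gave 6%.

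**Both paths together** (r = 0.15, phi = 0.4, R = 0.2; random-intercept model, uncorrelated person means). Rejection was 88% with neither term, 27% with prior sitting only, 48% with time only, and 5% with both. With opposite time-of-day signs the paths partly cancel, and the unadjusted rate is 10%.

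**The mirror direction.** Suppose earlier affect drives sitting, affect persists, and sitting has no effect on affect. A behavior-to-affect model without earlier affect then rejects 14–16%, 45% and 87% at the same three (r, phi) settings. Adjusting one direction only would leave the other exposed.

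**The case against.** The strongest reply is that the plan promises little. The SAP speaks of associations and the protocol calls the work exploratory. For a marginal or predictive target, the association of affect with later sitting is real even when it arises through earlier sitting. This stands. Under that target the models are under-described, not wrong, and adjusting for prior sitting changes the quantity being estimated.

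A second reply is that the percentages rest on a model and inputs the documents do not contain. The SAP names no random effect, residual structure, alpha or centring. This also stands: the figures show how a mechanism works and do not measure this plan. A reader might take them as false-positive rates of Part A; the documents do not support that reading.

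A third is that time of day is listed in Aim 1 as a factor to study, not as a confounder. It can be both. Since the protocol already treats it as related to sedentary behavior, leaving it out of models for another time-varying factor needs a reason.

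A reader might also infer that the two directions are exactly one test, or that the data cannot address order in time. Neither follows. The identity is exact only for person-demeaned variables in a shared window, and activPAL with EMA times permits windowed models.

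**Conclusion.** The point holds in limited form. The Part A covariate list leaves moment-level confounding in place, and the models as written cannot support a statement about direction. They remain usable as descriptions of marginal association.

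The conclusion rests on two things: the four covariates are in effect fixed within a person over four weeks, and nothing else is listed. It does not rest on the simulated rates. The size of any bias is unknown. It is negligible if the induced correlation is well below about 0.02 and substantial if it approaches 0.1.

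Mixing of within- and between-person association through uncentred affect looks small. At r = 0.15 and phi = 0.4, simulated slopes were 0.059 to 0.072 against 0.060 within person, as the assumed between-person correlation rose from 0 to 0.8. Severity is low, because only the interpretation of exploratory Aim 1 is affected.

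**What to change.** 1. Add time of day and study day to all Part A models, and keep age, gender, race and job type.
2. Split each time-varying predictor into a person-centred part and a person mean.
3. For each direction, state the outcome, the window before or after the EMA, and whether the target is marginal or net of earlier values.
4. For affect to later behavior, report models with and without person-centred sitting in the 30 minutes before the EMA, together with its person mean. The 30 minutes follows the SAP's PART B.
5. For behavior to later affect, report models with and without the affect from the previous EMA of the same day, given equal standing with item 4. That EMA may be hours earlier, so say that it adjusts only partly.
6. If these models are not run, report associations and claim no direction.

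**Cost.** SAP wording and a few extra models; no new measurement.
- **Precision.** In the affect-to-behavior simulations, the standard error of the within-person slope rose by about 3% at r = 0.2, phi = 0 (0.0324 to 0.0333). It fell by about 11% at r = 0.2, phi = 0.5 (0.0322 to 0.0288).
- **Degrees of freedom.** The two person means use 2 of at most 15 between-person degrees of freedom (20 people − 1 intercept − at least 4 covariate terms).
- **Missing prior activPAL data.** "The activPAL will be dropped off every Monday morning and picked up every Friday of the same week", so some early Monday EMAs lack it. If one EMA per Monday is affected, that is 4 × 20 = 80 of 1,200 records (6.7%).
- **Lagged affect.** The first EMA of each day drops out, leaving at most 2 × 20 × 20 = 800 of 1,200 records.

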### *PART B*

For instances where prompts were sent and a response occurred, the response time will be recorded (seconds) and the average response time calculated. The number of responses occurring each hour will be calculated to identify the frequency of responses by hour. Generalized estimating equations (GEEs) will be ran using GENMOD (with a repeated statement) to examine the main effect of prompt delivery (sent or not sent) by modeling the mean likelihood of a response as an odds ratio, over the next 5-minute and 30-minute periods. An autoregressive model will be used to account for time dependency and the correlation between observations. Mixed model analyses will be conducted using PROC MIXED to examine the association between prompt type and total sedentary time over the next 5-minute and 30-minute period. All models will be adjusted for age, race, gender, day of intervention and minutes of sitting 30 minutes prior to a prompt. Decision points where the participant was standing or moving at the time of prompt delivery (sent) or scheduled (not sent) time will be excluded from analyses.

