## Inclusion criteria:

Full-time employees, males or females, ages 18-65, with sedentary working habits (as indicated by >7 hrs/day of sedentary time at work in the Sedentary Behavior Questionnaire), and are willing to engage in the study assessment and intervention for 10 weeks.

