**Part B (weeks 5-9):**

Participants will be randomized to either receive or not to receive prompts every work hour (8 per day) via email, for 4 weeks. A total of 80 prompts will be sent to participants over a 4-week period during their work hours (9AM-5PM) on workdays.

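### The hourly response count needs seated decision points as its denominator, and response time needs a named window and a censored summary rather than a responder-only mean

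*SAP*

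**What the plan says.** The SAP, Part B, plans two descriptive results before the models. The first is response time: "For instances where prompts were sent and a response occurred, the response time will be recorded (seconds) and the average response time calculated". The second is the hourly summary: "The number of responses occurring each hour will be calculated to identify the frequency of responses by hour". Neither sentence names a window, and the second gives no denominator.

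The models come next. The GEE compares sent with not-sent decision points "by modeling the mean likelihood of a response as an odds ratio, over the next 5-minute and 30-minute periods". The covariate list has no term for hour of day: "All models will be adjusted for age, race, gender, day of intervention and minutes of sitting 30 minutes prior to a prompt". The section ends with the restriction to seated decision points: "Decision points where the participant was standing or moving at the time of prompt delivery (sent) or scheduled (not sent) time will be excluded".

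On the design, the protocol (Section 7, Part B) states: "Participants will be randomized to either receive or not to receive prompts every work hour (8 per day) via email, for 4 weeks". It also states: "A total of 80 prompts will be sent to participants over a 4-week period during their work hours (9AM-5PM) on workdays". No balancing of sent prompts within an hour slot is described. Aim 2 (Section 2) sets the primary outcome as a change from sitting to standing within 5 minutes.

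The SAP does not define a response. Here it is read as a change of posture, because not-sent decision points are also modelled for a response and the primary outcome is a posture change.

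**The concern.** The stated purpose of the hourly summary is how often responses occur at different hours. Every hour has the same number of scheduled decision points, but only seated ones count, and the seated share may differ by hour, for instance around lunch or meetings. The number of prompts sent in an hour can also vary by chance. An hour with few responses may have had fewer seated people, fewer prompts, or a lower response risk, and a bare count does not say which. The seated number per hour is not a planned output, so a reader could not recover the rate.

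The response-time mean has a different weakness. It covers only decision points that had a response, so its size is set mostly by the window, and ordinary standing alone gives a plausible-looking value. With no hour term in any model and no time-to-response analysis, these two summaries are the only planned results broken down by hour or reporting latency directly.

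**Working it through.** **Inputs from the documents.** 20 participants (Protocol, Section 5). 8 decision points per workday and 80 prompts (Section 7, Part B), with the 80 read as per participant. 20 workdays in four weeks, stated for Part A and assumed for Part B. Entry requires sedentary working habits, "as indicated by >7 hrs/day of sedentary time at work in the Sedentary Behavior Questionnaire".

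**The plan's own figure.** 8 × 20 = 160 decision points per person. 80/160 = 0.50, so the 80 prompts fit a sending probability of one half (inferred, not stated). Each clock-hour slot has 20 × 20 = 400 decision points, about 200 of them sent.

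**Effect of the seated share on the count.** Expected count = seated sent decision points × response risk. Seven hours of an eight-hour day gives an average seated share of about 7/8 = 87.5%. Let one hour have share h and let the other seven keep the average, so each has (7 − h)/7. With equal risk everywhere, the shortfall in the low hour is 1 − h/[(7 − h)/7]. Counts below assume a 10% response risk in 5 minutes.

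| h (assumed) | Other hours | Shortfall at equal risk | Count, other hours vs low hour |
|---|---|---|---|
| 87.5% | 87.5% | 0% | 17.5 vs 17.5 |
| 85% | 87.9% | 3% | 17.6 vs 17.0 |
| 75% | 89.3% | 16% | 17.9 vs 15.0 |
| 65% | 90.7% | 28% | 18.1 vs 13.0 |
| 55% | 92.1% | 40% | 18.4 vs 11.0 |

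To show the same count as the others, an hour at 75% would need a risk 0.893/0.75 = 1.19 times higher, and an hour at 65% a risk 0.907/0.65 = 1.40 times higher. In a more extreme hypothetical, ranks reverse: 200 × 0.90 × 0.20 = 36 responses against 200 × 0.50 × 0.30 = 30, although the second hour has the higher risk.

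**Chance variation in prompts sent.** With 80 of 160 sent per person and no balancing by hour, the variance per slot is 20 × 0.25 × (140/159) = 4.40 per person. For 20 people it is 88.1, SD 9.4. The 95% range is 200 ± 18.4, or 182 to 218 (about ±9%).

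**Response time with no prompt effect.** Assume a constant standing rate L = −ln(1 − b)/30 per minute, where b is the probability of standing within 30 minutes. The responder mean in a window of T minutes is 1/L − T/(exp(LT) − 1).

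| b (assumed) | 5-minute risk | Responder mean, T = 5 | Responder mean, T = 30 |
|---|---|---|---|
| 10% | 1.7% | 149.6 s | 884 s |
| 30% | 5.8% | 148.5 s | 847 s |
| 50% | 10.9% | 147.1 s | 797 s |

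The mean sits near half the window whatever the rate.

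**Would a not-sent responder mean repair this?** Suppose not-sent points follow b = 10% and sent points follow b = 50%. The 5-minute risk rises from 1.7% to 10.9%, an odds ratio of (0.1091/0.8909)/(0.0174/0.9826) = 6.9, yet the responder means differ by 149.6 − 147.1 = 2.5 s. The means separate clearly only if the prompt acts as a fast trigger. If 10% of sent prompts also trigger standing after a mean of 1 to 2 minutes (assumed), the 5-minute sent mean is 70 to 120 s, which is 27 to 79 s below the not-sent mean. Cumulative response curves over all seated points show both forms of effect. In the first case they reach 1.7% against 10.9% at 5 minutes and 10% against 50% at 30 minutes.

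**Precision of the hourly share.** Seated sent points per hour: 200 × 0.875 = 175. The half-width is 1.96 × √(p(1 − p)/175): 2.1 points at p = 2%, 4.4 at 10% and 5.9 at 20%, before clustering.

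**The case against.** The best defence is that the summaries are descriptive and carry no inference. A count correctly describes when responses occurred, the SAP claims no ranking or test by hour, scheduled points are equal in every hour, and nothing bars printing denominators. All of that stands. It limits the weight of the point, but a count without the seated number still does not give a frequency relative to opportunity.

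The artefact is also small against noise. For 18 versus 15 responses at 10% risk, the 95% sampling error of the difference is 1.96 × √(17.9 × 0.9 + 15.0 × 0.9) ≈ 11. This stands too: a denominator removes a distortion but does not make small hourly differences readable.

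On the window, the 5-minute primary outcome and the SAP's 5- and 30-minute periods narrow the choice to two. Those two give no-effect means of about 150 s and 800 to 880 s, so the window should still be named.

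A reader might infer more than the documents support in three ways:
- That the prompt effect is biased or lacks a comparator. It does not: the GEE compares sent with not sent at 5 and 30 minutes, and that already shows whether standing comes sooner after a prompt.
- That placing a not-sent responder mean beside the sent one would isolate prompted standing. It would not. Responding occurs after randomization, so the two groups are selected, and the working shows a sixfold difference in risk almost vanishing.
- That seated shares do differ widely by hour. No hourly shares are given, and the entry criterion makes very low shares less typical.

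**Conclusion.** The point holds as a minor improvement to two descriptive results. The hourly count confounds opportunity with response risk. The distortion is nil if seated shares are equal across hours, 3% at 85% seated, 16% at 75% and 28% at 65%, with about ±9% more from chance variation in prompts sent. The responder-only mean response time says little until its window is named, and even then it is a poor guide to a prompt effect.

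The magnitudes rest on assumptions: seated shares by hour, response risks, a constant standing rate, 80 prompts per participant, and 20 workdays in Part B. The 87.5% average comes from a self-reported entry threshold. That the count lacks a denominator and the mean lacks a window rests on the text alone. No model, primary analysis or primary conclusion is affected.

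**What to change.** Reword two sentences in the SAP, Part B.

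1. **Hourly summary.** By clock hour, report the share of seated decision points with a response within 5 minutes, showing numerator and denominator, separately for sent and not sent. The 30-minute window may be added. Label the table descriptive, with no hourly test.
2. **Response time.** Name the window. Replace the responder-only mean with a censored time-to-response summary over all seated decision points, or add that summary to it. Cumulative response curves to 30 minutes, sent and not sent, would serve, measured from the delivered time for sent points and the scheduled time for not-sent points. If the mean is kept, state that it describes responders only, and do not compare it between conditions as evidence of a prompt effect.

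The cost is one slightly larger table and one figure, from activPAL data that the protocol already collects in the prompt weeks. The downside is imprecise hourly cells, about 2 to 6 points half-width for risks of 2% to 20%, before allowing for clustering within 20 people. The GEE and mixed models stay as written.
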